9.2.6. Pregnancy

- Details of all pregnancies in female participants will be collected after the start of study treatment and until the last follow-up visit.
- If a pregnancy is reported, the investigator should inform GlaxoSmithKline (GSK) within 2 weeks of learning of the pregnancy and should follow the procedures outlined in Appendix 5.
- Abnormal pregnancy outcomes (eg, spontaneous abortion, fetal death, stillbirth, congenital anomalies, ectopic pregnancy) are considered SAE.

9.3. Treatment of Overdose

An overdose is defined as a dose greater than the total doses described above which results in clinical signs and symptoms. These should be recorded by the Investigator on the AE/SAE eCRF pages.

The dose of GSK3772847 considered to be an overdose has not been defined. There are no known antidotes and GlaxoSmithKline does not recommend a specific treatment in the event of a suspected overdose. The Investigator will use clinical judgement in treating the symptoms of a suspected overdose.

In the event of an overdose, the investigator should:

- 1. Contact the Medical Monitor immediately.
- 2. Closely monitor the participant for AE/SAE and laboratory abnormalities for 16 weeks after the last dose.
- 3. Obtain a serum sample for PK analysis within 7 days from the date of the last dose of study treatment if requested by the Medical Monitor (determined on a case-by-case basis).
- 4. Document the quantity of the excess dose as well as the duration of the overdosing in the eCRF.

Decisions regarding dose interruptions or modifications will be made by the investigator in consultation with the Medical Monitor based on the clinical evaluation of the participant.

9.4. Safety Assessments

Planned time points for all safety assessments are provided in the SoA.

9.4.1. Physical Examinations

- A complete physical examination will include, at a minimum, assessments of the Skin, Cardiovascular, Respiratory, Gastrointestinal and Neurological systems. Height and weight will also be measured and recorded.
- Investigators should pay special attention to clinical signs related to previous serious illnesses.

9.4.2. Vital Signs

Vital signs should be performed at the time points specified in the Schedule of Activities (SoA) table (Section 2) prior to conducting spirometry. Blood pressure (systolic and diastolic) and pulse rate will be measured in the supine position after approximately 5 minutes rest. A single set of values will be collected and recorded in the source documentation and eCRF.

9.4.3. Electrocardiograms

All sites will use standardised ECG equipment provided by a centralized external vendor. A single 12-lead ECG and rhythm strip will be recorded after measurement of vital signs and before other clinical tests such as blood draws and pulmonary function tests. Recordings will be made at the time-points defined in the Schedule of Activities (SoA) table (Section 2). All ECG measurements will be made with the participant in a supine position having rested in this position for approximately 5 minutes before each reading. Participants should be reminded to avoid caffeine or caffeinated drinks for at least 8 hours before each 12-lead ECG assessment. Also, decongestants are disallowed for at least 24 hours and antihistamines for at least 48 hours before each 12-lead ECG assessment.

For participants who meet the QTc, protocol defined stopping criteria, triplicate ECGs (over a brief period of time) should be performed (Section 8).

The Investigator, a designated sub-Investigator or other appropriately trained site personnel will be responsible for performing each 12-lead ECG. The Investigator must provide his/her dated signature on the original paper tracing, attesting to the authenticity of the ECG machine interpretation.

All ECGs will be electronically transmitted to an independent cardiologist and evaluated. The independent cardiologist, blinded to treatment assignment, will be responsible for providing measurements of heart rate, QT intervals and an interpretation of all ECGs collected in this study. A hard copy of these results will be sent to the Investigator. The Investigator must provide his/her dated signature on the confirmed report, attesting to his/her review of the independent cardiologist's assessment.

Details of the cardiac monitoring procedures will be provided by the centralized cardiology service provider.

9.4.4. Continuous ambulatory ECG (Holter)

Continuous ECG monitoring (Holter) assessments have been added to the protocol to allow for a quantitative assessment of abnormal rhythm events. Holter monitors will be provided by a third party vendor to each site. The device should be connected and electrodes attached to the participant as per the vendor's instructions.

9.4.5. Clinical Safety Laboratory Assessments

- Refer to Appendix 2 for the list of clinical laboratory tests to be performed and to the SoA for the timing and frequency.
- The investigator must review the laboratory report, document this review, and record any clinically relevant changes occurring during the study in the AE section of the eCRF. The laboratory reports must be filed with the source documents. Clinically significant abnormal laboratory findings are those which are not associated with the underlying disease, unless judged by the investigator to be more severe than expected for the participant's condition.
- All laboratory tests with values considered clinically significantly abnormal
 during participation in the study or within 5 days after the last dose of study
 treatment should be repeated until the values return to normal or baseline or are
 no longer considered significantly abnormal by the investigator or medical
 monitor.
- If such values do not return to normal/baseline within a period of time judged reasonable by the investigator, the etiology should be identified and the sponsor notified.
- All protocol-required laboratory assessments, as defined in Appendix 2, must be conducted in accordance with the laboratory manual and the SoA.
- If laboratory values from non-protocol specified laboratory assessments performed at the institution's local laboratory require a change in participant management or are considered clinically significant by the investigator (eg, SAE or AE or dose modification), then the results must be recorded in the eCRF.

9.5. Pharmacokinetics

- Whole blood samples of approximately 3 mL will be collected for measurement
 of serum concentrations of GSK3772847as specified in the SoA. The timing of
 PK samples may be altered and/or PK samples may be obtained at additional time
 points to ensure thorough PK monitoring. The actual date and time (24-hour clock
 time) of each sample will be recorded.
- Samples will be used to evaluate the PK of GSK3772847. Samples collected for analyses of serum concentration may also be used to evaluate safety or efficacy aspects related to concerns arising during or after the study.
- Instructions for the collection and handling of biological samples will be provided in the SRM

9.6. Pharmacodynamics

Pharmacodynamic (PD) Biomarkers

Blood (serum) samples will be collected during this study for the purposes of measuring free and total sST2 levels. Samples will be collected at the time points indicated in the SoA. The timing of the collections may be adjusted on the basis of emerging PK or PD

data from this study or other new information in order to ensure optimal evaluation of the biomarker endpoints.

9.7. Genetics

Information regarding genetic/ pharmacogenetic (PGx) research is included in Appendix 6. The IEC/IRB and, where required, the applicable regulatory agency must approve the PGx and genetic assessments before these can be conducted at the site. The approval(s) must be in writing and will clearly specify approval of the PGx and genetic assessments (i.e., approval of Appendix 6).

In some cases, approval of the PGx and genetic assessments can occur after approval is obtained for the rest of the study. If so, then the written approval will clearly indicate approval of the PGx and genetic assessments is being deferred and the study, except for PGx and genetic assessments, can be initiated. When PGx and genetic assessments will not be approved, then the approval for the rest of the study will clearly indicate this and therefore, PGx and genetic assessments will not be conducted.

9.8. Biomarkers

9.8.1. Exploratory Biomarkers

Blood (serum) and sputum (Section 9.8.1.1) samples will be collected during this study and may be used for the purposes of measuring asthma biomarkers or endotypes of asthma, as well as response to GSK3772847. Biomarkers will include, but not be limited to, serum total IgE, Eosinophilic Cationic Protein (ECP) and Type-2 chemokines (e.g. CCL13, CCL17) as well as sputum cell counts (e.g. percentage eosinophils). Samples may also be used to identify factors that may influence the development of asthma and/or medically related conditions. Samples will be collected at the time points indicated in the SoA.

9.8.1.1. Sputum Sub-Study

At selected sites only, consenting participants who are eligible for randomisation at Visit 2 will be entered into the Sputum sub-study. In a subset of approximately 50% of eligible participants, sputum samples will be collected as specified in the SoA. The participants in the Sputum Sub-Study will be randomised equally in the two treatment groups.

Details of the sputum collection and processing methodology will be provided in the SRM.

9.8.2. Immunogenicity Assessments

Serum samples will be collected and tested for the presence of antibodies that bind to GSK3772847, as specified in the SoA. The actual date and time (24-hour clock time) of each sample will be recorded.

The presence of anti-GSK3772847 antibodies will be assessed using a tiered approach including a screening assay, a confirmation assay and calculation of titre.

Instructions for the collection and handling of biological samples will be provided in the SRM.

9.9. Health Economics OR Medical Resource Utilization and Health Economics

Health Economics/Medical Resource Utilization and Health Economics parameters are not evaluated in this study.

10. STATISTICAL CONSIDERATIONS

10.1. Hypotheses

The primary null hypothesis (H_0) for this study is that the ratio of the proportions of subjects with loss of asthma control from randomization to Week 16 between GSK3772847 and placebo is unity.

$$H_0 \colon \frac{Proportion\ with\ loss\ of\ asthma\ control\ at\ Week\ 16\ on\ GSK3772847}{Proportion\ with\ loss\ of\ asthma\ control\ at\ Week\ 16\ on\ Placebo} = 1$$

The alternative hypothesis (H_1) for this study is that the ratio of the proportions of subjects with loss of asthma control from randomization to Week 16 between GSK3772847 and placebo is not unity.

$$\textit{H}_{1} : \frac{\textit{Proportion with loss of asthma control at Week 16 on GSK3772847}}{\textit{Proportion with loss of asthma control at Week 16 on Placebo}} \neq 1$$

The hypothesis will be tested by calculating the posterior probability that the ratio of the proportion of subjects with loss of asthma control on GSK3772847 compared with placebo is less than 1.0, 0.75, 0.5 and 0.2 (i.e. a 0%, 25%, 50% and 80% reduction) and supported by an estimate of the ratio with a 95% credible interval. A non-informative prior will be used.

Although the success of the study will be assessed by calculating posterior probabilities of the treatment effect reaching various thresholds and not statistical significance, a frequentist analysis will also be performed testing the above hypothesis.

10.2. Sample Size Determination

The study will randomize 74 participants per treatment arm with the aim of having 70 evaluable participants per arm. For the purpose of this study an evaluable participant is defined as a participant who completes the Week 16 clinic visit whilst remaining on IP or who withdraws from IP having met the primary endpoint. See Section 10.4.1 for how subjects who withdraw early from IP for reasons other than loss of asthma control are handled in the analysis.

In addition to testing the hypothesis in the overall population, the study will randomize a sufficient number of participants to evaluate trends in pre-defined subgroups (e.g. eosinophil strata).

The true proportion of participants that would experience a loss of asthma control on each treatment is unknown. However in a similar study of Dupilumab compared with placebo, the proportion of participants with loss of control were 6% and 44% for Dupilumab and placebo respectively. Table 4 gives the power to detect a statistically significant difference (at the two-sided 5% level) between the two treatments assuming the true proportion with loss of control on placebo is 44% and the true proportion with loss of control on active is 6%, 11%, 19% and 22% [Fleiss, 2003].

Table 4 Table of Power Achievable for Different Treatment Comparisons using N=70 per arm calculated using PASS

True proportion on Placebo	True proportion on GSK3772847	Reduction	Power
44%	6%	86%	> 99%
44%	11%	75%	> 99%
44%	19%	57%	90%
44%	22%	50%	80%

Assuming the true proportion with loss of control on placebo is 44%, then with 70 evaluable participants per arm, the study will have at least 80% power to detect a statistically significant difference between treatments assuming the true proportion with loss of control on GSK3772487 is at most 22% (Table 4).

With 70 evaluable participants per arm and assuming the true proportion with loss of control on placebo is 44%, the smallest observed difference that would lead to rejection of the null hypothesis (minimum detectable effect) is 31% corresponding to a proportion with loss of control on GSK3772847 of 28%.

There is a single primary endpoint so no adjustments are required for multiplicity.

10.3. Populations for Analyses

For purposes of analysis, the following populations are defined:

Population	Description
Enrolled	All participants who sign the ICF.
Randomized	All participants who were randomized. A subject who is recorded as a screen or run-in failure and also randomized will be considered to be randomized in error provided they have not performed any study assessments.
Modified Intent-to-treat (mITT)	All randomized subjects who take at least 1 dose of study treatment. Participants will be analyzed according to the treatment they actually

Population	Description
	received.
PK	All randomized subjects who received at least one dose of study medication, and for whom at least one pharmacokinetic sample was obtained, analyzed and was measurable.

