7. TREATMENTS

Study treatment is defined as any investigational treatment(s), marketed product(s), placebo, or medical device(s) intended to be administered to a study participant according to the study protocol.

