10.4. Statistical Analyses

10.4.1. Efficacy Analyses

All efficacy analyses will be performed on the mITT Population.

Endpoint	Statistical Analysis Methods
Primary	The primary endpoint proportion of subjects with loss of asthma control will be analyzed using both Bayesian and Frequentist methods. A subject is deemed to have met the endpoint of loss of asthma control if they meet the criteria for any of the components of the definition of loss of asthma control.
	The posterior probabilities that the ratio of the proportion of subjects with loss of asthma control on GSK3772847 compared with placebo is less than 1.0, 0.75, 0.5 and 0.2 (i.e. a 0%, 25%, 50% and 80% reduction) will be calculated analytically assuming a non-informative prior. This will be supported by an estimate of the ratio with a 95% credible interval. Results will also be presented for the two eosinophils strata separately.
	In addition, the proportion of participants with loss of asthma control will be analyzed using logistic regression allowing for baseline eosinophils strata. The odds ratio, 95% CI and p-value for the comparison of GSK3772847 with placebo will be presented.
	Results will also be presented for the two eosinophils strata separately by fitting a separate model with an additional term for eosinophil strata by treatment interaction. The effect of eosinophils as a continuous covariate will also be examined in a separate-logistic regression model.
	 Missing data will be handled using the following methods: 1) The loss of asthma control will be set to missing for participants who withdraw from IP prior to Week 16 for reasons other than loss of asthma control 2) A sensitivity analysis will be performed where participants who withdraw from IP prior to Week 16 for reasons other than loss of asthma control will have the endpoint set to loss of control
Secondary	The following secondary endpoints will be analyzed using the same statistical analysis as described for the primary endpoint: • Proportion of participants with a clinically significant asthma exacerbation

Endpoint	Statistical Analysis Methods
	 (requiring OCS and/or hospitalisation) Proportion of participants with Pre-bronchodilator FEV1 decrease from Baseline (measured at the end of Run-in) >7.5 % Proportion of participants with Inability to titrate inhaled corticosteroid

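### The mITT set used for every efficacy analysis assigns participants by treatment actually received; efficacy should be by randomised arm, with entry by a dose of double-blind IP

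*Protocol*

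**What the plan says.** Section 10.3 gives the mITT population two properties. Membership is "All randomized subjects who take at least 1 dose of study treatment". Assignment is "Participants will be analyzed according to the treatment they actually" received. Section 10.4.1 then states: "All efficacy analyses will be performed on the mITT Population". Section 10.4.2 uses the same set for safety. Section 10.3 also defines a Randomized population, but Section 10.4 uses it for no efficacy analysis.

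Section 7 sets the meaning of the entry term: "Study treatment is defined as any investigational treatment(s), marketed product(s), placebo" and devices also count. The Section 7.1 table lists fluticasone/salmeterol and fluticasone as study treatments beside the antibody and saline.

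On withdrawals whose cause is not loss of control, Section 10.4.1 says: "The loss of asthma control will be set to missing for participants who withdraw from IP prior to Week 16". A sensitivity analysis is planned in which these participants "will have the endpoint set to loss of control". Section 10.2 sizes the trial on that footing: "The study will randomize 74 participants per treatment arm with the aim of having 70 evaluable participants per arm", where evaluable means someone who "completes the Week 16 clinic visit whilst remaining on IP or who withdraws from IP having met the primary endpoint".

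**The concern.** Randomisation protects a comparison only while participants stay in the arm to which they were randomised. Assignment by product received is the usual convention for safety tables. For efficacy it lets an event after randomisation, a preparation or dispensing error, decide which arm a participant counts in. If such errors are related to prognosis or to site, the primary contrast is no longer protected. The rule also leaves open which arm applies to someone given active product at one of the four infusions and saline at another.

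The entry wording adds a smaller ambiguity. Read literally, everyone randomised after the run-in has already had a dose of study treatment. A participant who was randomised but never infused would enter the efficacy set with no actual double-blind arm.

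**Working it through.** **Inputs.** 1:1 allocation (Section 7.3). From Section 10.2: 74 randomised and 70 evaluable per arm, 44% loss of control on placebo, 6%, 11%, 19% or 22% on active, two-sided 5%.

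**The plan's own figures.** Pooled-variance normal approximation: power = Φ{[d − 1.96·√(2p̄(1−p̄)/n)] / √[(p₁(1−p₁)+p₂(1−p₂))/n]}, where d = p₁ − p₂ and p̄ is their mean. With n = 70 and 44% against 6%, 11%, 19% and 22%, this gives 99.98%, 99.5%, 89.8% and 79.7%. Table 4 states >99%, >99%, 90% and 80%, so it reproduces. The planned non-evaluable share is 4/74 = 5.4% per arm, and 70/(1 − 4/74) = 74.

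**Size of the by-received rule.** Assume m participants in each arm are given the other arm's product and respond to what they received. By randomised arm, with 74 per arm:

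- active = [(74 − m)·0.22 + m·0.44]/74
- placebo = [(74 − m)·0.44 + m·0.22]/74

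For m = 1: active = 16.50/74 = 0.223, placebo = 32.34/74 = 0.437, ratio 0.51.

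| Swapped pairs | Ratio, by randomised arm | Power | Ratio, by treatment received | Power |
|---|---|---|---|---|
| 0 | 0.50 | 81.9% | 0.50 | 81.9% |
| 1 | 0.51 | 79.7% | 0.50 | 81.9% |
| 2 | 0.52 | 77.4% | 0.50 | 81.9% |
| 4 | 0.54 | 72.3% | 0.50 | 81.9% |

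The values of m are assumptions; the protocol gives no dosing-error rate. The two analyses differ by about 0.01 on the ratio and 2 points of power per swapped pair, and not at all when m = 0.

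**One participant at the significance boundary.** Take 31/70 placebo against 19/70 active by randomised arm: pooled proportion 0.357, SE 0.0810, z = 2.12, p = 0.034. If one placebo participant with an event had received active, the by-received analysis has 30/69 against 20/71: z = 1.89, p = 0.059. With flat priors, the posterior probability that the ratio is below 1 moves from 0.982 to 0.970, and below 0.75 from 0.79 to 0.72.

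**The withdrawal rule, for scale.** Let the planned 8 non-evaluable participants split between the arms as assumed below, with 22% and 44% among the rest. The complete-case ratio is 0.50 throughout. Counting the withdrawals as loss of control, with 74 per arm:

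- 4 active, 4 placebo: 26.2% against 47.0%, ratio 0.56, power 75.3%
- 6 active, 2 placebo: ratio 0.62, power 58.3%
- 8 active, 0 placebo: ratio 0.69, power 39.9%

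The planned sensitivity analysis therefore responds strongly to an imbalance between the arms.

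**The case against.** **Against the by-received point.** Allocation is central through an interactive web system (Section 7.3) and a dedicated unblinded preparer makes up each infusion (Section 7.5), so swaps should be rare. The first infusion is on the day of randomisation, Section 6.6 ties entry to the treatment period to receiving double-blind treatment, and the Schedule of Activities labels the IP as the double-blind study treatment. Few participants could be randomised and never infused, and most readers would take the entry rule as intended. All of this stands. It limits the size of the problem but does not make the text correct.

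**The p-value example.** A reader might infer from 0.034 against 0.059 that one error could decide the trial. The case is chosen at the boundary and moves the result against the drug. Section 10.1 also says that success rests on posterior probabilities and not on significance, and those move little.

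**The withdrawal rule.** A reader might also infer that setting other withdrawals to missing invalidates the primary analysis. It can bias the result: with no true effect, all 8 withdrawals on active and an assumed risk of 66% to 100% in those removed, the complete-case ratio would be 0.94 to 0.85. The documents give no basis for expecting such a split. The Phase 1 Part 2 reports of non-sustained ventricular tachycardia in the risk table are 3 among 18 + 11 = 29 on active (10.3%) and 1 among 6 + 4 = 10 on placebo (10.0%), which is balanced. That rate does not carry over directly either, because screening ECG and Holter findings exclude participants here. Even at about 66 evaluable per arm, power at 22% is 77.3% against 79.7%. The evaluable basis is disclosed in Section 10.2, the worst-case sensitivity analysis is specified, and the Kaplan-Meier analysis keeps these participants as censored.

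**Origin.** It is tempting to blame the current amendment, which dropped the separate Safety population. Both earlier protocol versions bound in the same file already have the by-received rule, with the Safety population identical to it.

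**Conclusion.** The point holds as a wording defect in Sections 10.3 and 10.4.1. The current text makes every efficacy analysis as-treated, and the literal entry criterion can be met before any infusion. The consequence is nil without dosing errors. With them it is about 0.01 on the ratio and 2 points of power per swapped pair, assuming the design rates, 74 per arm and swaps unrelated to prognosis. Errors related to prognosis could do more harm, but the protocol gives nothing from which to size that. This is a should-fix. The documents do not support going further and requiring a different primary method for withdrawals: that is a choice of estimand, already accompanied by a sensitivity analysis.

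**What to change.** In Section 10.3, define the efficacy population as all randomised participants who received at least one dose of double-blind IP, analysed by randomised treatment. State separately that safety summaries go by treatment actually received. Refer to both rules in Sections 10.4.1 and 10.4.2. The cost is a few words in the protocol and the analysis plan, with no new data and no change to visits, dosing or sample size.

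Optionally, report the ratio of Week 16 Kaplan-Meier risks as a further sensitivity analysis. It uses the time-to-loss-of-control data already planned.
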